Patient-reported Adverse Events From Osteopathic Manipulative Treatment

Study Protocol and Statistical Analysis Plan

NCT02386085

07/10/2014

PATIENT-REPORTED ADVERSE EVENTS FROM OSTEOPATHIC MANIPULATIVE TREATMENT

STUDY PROTOCOL

A prospective observational cohort study design will be used to accomplish the specific aims of the proposed study. Patients receiving OMT at one of the research sites will receive a coded information packet inviting them to participate in the study. Patients will have the option of completing the 24-hour, 72-hour, and 1-week survey either electronically or using the paper surveys included in the information packet. The clinician will provide documentation of the diagnoses, osteopathic technique(s) used, and body region(s) treated for all patients who complete the 24-hour survey.

i. Participants

DO-Touch.NET members will be recruited to join the proposed study as a research site. The goal is to have at least 50 clinicians contributing to this study. All patients from the research sites who receive OMT and who are age 18 years and above will be eligible to participate in the proposed study. Patients who are unable to communicate in English, Spanish, French, German, or Portuguese will be excluded. Participation is voluntary and informed consent will be elicited from eligible patients prior to their completion of the surveys. A total of 1000 participants will be included in the study.

ii. Recruitment and Procedures

An informational poster will be placed in the waiting room to introduce the study to the patients being seen that day. Following completion of their office visit, eligible patients will be provided an informational packet with a unique code number, paper copies of the surveys, and instructions on how to access the online survey. The code will be recorded by the staff on a tracking sheet to facilitate linking the patient-reported data on adverse events with the clinic treatment documentation.

Informed consent will be obtained as the first page of the 24-hour survey and will include consent for the clinician who treated the patient to provide de-identified documentation of the OMT provided. Participants completing the 24-hour survey online who provide their email address will receive an automated invitation to complete the 72-hour and 1-week surveys. Participants who choose to complete the surveys on paper will be provided a postage-paid envelope to return the surveys to the central coordinating center. Participants who complete all 3 surveys will receive \$10 in the form of a gift card or money order.

When a participant completes the 24-hour survey online or when a completed survey packet is received, the network manager at the central coordinating center will inform the research site that they need to provide documentation of the OMT from the corresponding patient-encounter including the diagnoses treated with OMT, what techniques were performed on that patient, and the clinician's assessment of patient response to the treatment.

iii. Data Collection Instruments

Study data will be collected and managed using REDCap electronic data capture tools hosted at A.T. Still University. Data from participants that is submitted using paper surveys will be entered into REDCap at the central coordinating center.

Patient-reported Adverse Events: Basic demographic information (i.e., sex, age, race, and ethnicity) will be obtained from participants at the beginning of the 24-hour survey. The 24- and 72-hour surveys will assess the severity, duration, and location of potential adverse events including pain or discomfort, stiffness, unexpected tiredness or fatigue, headache, light headedness, numbness or tingling, muscle weakness, difficulty talking, vision disturbance, tinnitus, nausea or vomiting, problems sleeping, irritability or crying, and difficulty walking. Participants will also be able to add other potential adverse events to the list. They will be asked to assess whether the symptom is definitely, probably, possibly, unlikely, or not related to the OMT received. Additionally, the 24- and 72-hour surveys will assess the existence of these symptoms within the week prior to treatment and whether the participants have sought urgent care, visited the emergency room, or been hospitalized. The 1-week survey will follow-up on adverse events reported on the 72-hour survey. The timing of these surveys is designed to provide information regarding whether the onset of adverse events after OMT is immediate (<24 hours) or delayed (24-72 hours) and whether the duration is short (<72 hours), medium (≥72 hours but less than 1 week), or long (≥1 week).

Documentation of OMT: Documentation of the OMT provided will consist of a standard matrix of checkboxes designating which osteopathic technique(s) were used in which body region(s). The potential osteopathic techniques include articulatory/still, balanced ligamentous tension/ligamentous articular strain, osteopathy in the cranial field, counterstrain/facilitated positional release, high velocity/low amplitude (thrust), indirect/functional method, muscle energy, myofascial release, soft tissue, and visceral. An area will be provided to describe techniques used which are not included in any of these technique groupings. The standard 10 body regions (head/face, neck, thoracic, ribs, lumbar, sacrum, pelvis, abdomen/other, upper extremities, and lower extremities) will be included in the matrix. For each region treated, the physician will be asked to quantify the patient's response to treatment as resolved, improved, unchanged, or worsened.

STATISTICAL ANALYSIS PLAN

The de-identified data will be downloaded from the REDCap system at the end of data collection. The incidence of each adverse event will be estimated from the entire sample using 95% confidence intervals obtained by fitting generalized linear mixed models to account for the clustering of responses from patients treated by the same clinician. Additionally, generalized linear mixed models will be used to test whether certain techniques or body regions have higher incidence of adverse events than others.

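### Prior OMT exposure is not among the described data items, so incidence pools first-time and returning patients in an unknown mix and the technique and region comparisons may be confounded by it

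*Combined protocol and SAP*

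**What the plan says.** Section i (Participants) of the protocol admits adults whatever their treatment history: "All patients from the research sites who receive OMT and who are age 18 years and above will be eligible to participate". The only exclusion it states concerns language: "Patients who are unable to communicate in English, Spanish, French, German, or Portuguese will be excluded". The target is fixed: "A total of 1000 participants will be included in the study", from a hoped-for 50 or more clinicians.

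Section iii (Data Collection Instruments) gives the patient background items as a closed list: "Basic demographic information (i.e., sex, age, race, and ethnicity) will be obtained from participants at the beginning of the 24-hour survey". The surveys also cover the severity, duration and location of each symptom, the patient's view of its relation to OMT, and use of urgent, emergency or hospital care. One item looks back before the visit: "the 24- and 72-hour surveys will assess the existence of these symptoms within the week prior to treatment".

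Section ii (Recruitment and Procedures) says the clinician supplies documentation "including the diagnoses treated with OMT, what techniques were performed on that patient, and the clinician's assessment of patient response to the treatment". Section iii adds a grid of techniques by body region and a rating of response for each region treated.

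The Statistical Analysis Plan estimates the incidence of each event over all participants, with mixed models for clustering by clinician. It then states that "generalized linear mixed models will be used to test whether certain techniques or body regions have higher incidence of adverse events than others". It names no patient-level covariate.

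**The concern.** A patient at a first OMT visit and one at a repeat visit may not carry the same risk. Someone who reacted badly may be less likely to return, and a clinician who knows how a patient responded can choose techniques accordingly. Packets are handed out after office visits, so a patient who attends often has more chances to receive one than a patient who came once.

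Both stated analyses are exposed. The pooled incidence depends on a mix that the study would not observe. A reader who takes it as the risk of starting OMT has no means of checking that reading. In the technique and region models, a technique kept mainly for established patients could look safer, and one favoured at first visits riskier, with no true difference. Such a choice is made patient by patient within one clinician's practice, so a clinician clustering term does not remove it.

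**Working it through.** **Figures in the plan.** The documents give no share of returning patients, no event rate by OMT history and no technique use by OMT history. The target of 1000 comes without a derivation, so there is no plan figure to reproduce. Every rate and share below is an assumption.

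**Step 1: can any described item stand in for OMT history?**
- Sex, age, race and ethnicity: no.
- Symptoms in the week before treatment: these measure baseline symptoms, not earlier OMT.
- Relatedness and use of urgent, emergency or hospital care: these concern events, not earlier treatment.
- Diagnoses, techniques, regions and clinician-rated response: all describe the index encounter.

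None does.

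**Step 2: pooled incidence.** With share s returning, pooled = (1 − s) × p_first + s × p_return.

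| p_first | p_return | s | Pooled | Pooled minus p_first |
|---|---|---|---|---|
| 30% | 15% | 0.6 | 0.4 × 30 + 0.6 × 15 = 21% | −9 points |
| 30% | 15% | 0.8 | 0.2 × 30 + 0.8 × 15 = 18% | −12 points |
| 30% | 15% | 0.9 | 0.1 × 30 + 0.9 × 15 = 16.5% | −13.5 points |
| 20% | 15% | 0.8 | 0.2 × 20 + 0.8 × 15 = 16% | −4 points |
| 20% | 15% | 0.2 | 0.8 × 20 + 0.2 × 15 = 19% | −1 point |
| 20% | 20% | any | 20% | 0 |

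For scale, the 95% half-width at 20% incidence is 1.96 × √(0.20 × 0.80 / 1000) = 2.5 points. With 1000/50 = 20 patients per clinician and an assumed intraclass correlation of 0.05, the design effect is 1 + 19 × 0.05 = 1.95 and the half-width is 3.5 points. The gap can exceed the sampling error or sit inside it, depending on the assumptions.

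**Step 3: technique comparison with no true technique effect.** Take 200 first-time and 800 returning patients.

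- Risks 30% and 15%; technique used in 15% of first-time and 40% of returning patients. Users: 30 + 320 = 350, events 9 + 48 = 57. Non-users: 170 + 480 = 650, events 51 + 72 = 123. Odds ratio = (57/293) / (123/527) = 0.83.
- Same risks, usage reversed. Users: 80 + 120 = 200, events 24 + 18 = 42. Non-users: 120 + 680 = 800, events 36 + 102 = 138. Odds ratio = (42/158) / (138/662) = 1.28.
- Risks 20% and 15%, first usage pattern: 54/350 against 106/650, odds ratio = (54/296) / (106/544) = 0.94.
- Risks 20% and 15%, usage reversed: 34/200 against 126/800, odds ratio = (34/166) / (126/674) = 1.10.
- Equal risks, or equal usage in the two groups: odds ratio 1.00.

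Ignoring clustering, a two-sided 5% test would reject about 18% and 22% of the time in the first two cases, and about 7% in the two milder ones.

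**The case against.** The strongest reply is that the pooled estimate is coherent as it stands. The protocol enrols adults receiving OMT in these practices, and the SAP estimates incidence in those people. Nothing in the documents names patients new to OMT as the target. This stands: the pooled figure is valid for OMT patients as seen, and the problem arises only when it is read as the risk for a newcomer.

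A reader might go further and infer that patients who already tolerate OMT dominate the sample, push the incidence down and distort the technique results. The documents do not support that. They give no returning share and no sign that risk differs by history, so even the direction of the shift is assumed. Confounding of the technique comparison needs two conditions together: risk must differ by OMT history, and so must technique use. The worked example also treats technique as one yes/no exposure, whereas the form records several techniques across regions. The clinician term may absorb differences between practices in patient mix, but it does not remove confounding among the patients of one clinician.

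Two further replies stand in part. The instruments are summarised rather than reproduced, so the finding is that no described item captures OMT history. And sites hold a tracking sheet linking codes to encounters, so visit status might be recoverable, subject to what the consent covers. No such step is planned, and a site's own record need not show OMT given elsewhere.

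**Conclusion.** The concern holds in a limited form. Followed as described, the plan would not collect prior OMT exposure. The mix of first-time and returning patients could then be neither reported nor adjusted for, and the pooled incidence cannot be read as the risk for a patient new to OMT. Confounding of the technique and region comparisons is possible, not shown.

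The size is unknown. Under the assumptions above, the gap between pooled and first-visit incidence runs from nil to 13.5 points, and the spurious odds ratios are 0.83 and 1.28 in the stronger scenario, 0.94 and 1.10 in the milder one, and 1.00 if risks are equal. Confidence is high that the item is absent from the described content, and much lower about the size or direction of any effect. The change is worth making because, without the item, nobody can show which of these cases applies.

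**What to change.** Keep eligibility and the total of 1000 unchanged, and make three changes.

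1. Add one item to the 24-hour survey: *Was this your first OMT treatment ever? If not, about when was your last one?*
2. Report the incidence of each event for first-time and returning patients beside the pooled figure, and describe the pooled figure as incidence among OMT patients as seen in the participating practices.
3. In the SAP, name first-ever versus returning status, taken from this item, as the single pre-specified covariate for OMT history in the technique and region models.

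A clinician checkbox for first or return visit with that clinician is optional. It measures something different, since a patient who changed clinician is new to one and not to OMT, so it should serve only for sensitivity analysis.

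The cost is slightly more form burden and a wide interval in the first-time group. At an assumed 20% incidence, ignoring clustering, the half-width is 1.96 × √(0.16/200) = 5.5 points if 80% are returning (n = 200), and 1.96 × √(0.16/100) = 7.8 points if 90% are (n = 100).

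### Further OMT during follow-up is not recorded, so a reaction to a later visit can count as a delayed event of the index visit; repeat enrolment is a secondary gap.

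*Combined protocol and SAP*

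**What the plan says.** Under i. Participants, eligibility is open to any adult OMT visit: "All patients from the research sites who receive OMT and who are age 18 years and above will be eligible to participate". The only exclusion is language: "Patients who are unable to communicate in English, Spanish, French, German, or Portuguese will be excluded". There is no first-visit rule and no limit of one enrolment per person. The target is stated as "A total of 1000 participants will be included in the study", with "The goal is to have at least 50 clinicians contributing to this study".

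Under ii. Recruitment and Procedures, the identifier comes with the packet: "Following completion of their office visit, eligible patients will be provided an informational packet with a unique code number". Staff log the code on a tracking sheet, and the site later documents the OMT for the single encounter that matches the code.

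Under iii. Data Collection Instruments, the 24- and 72-hour surveys cover symptoms, their severity, duration and location, their presence in the week before treatment, a five-level rating of relatedness to the OMT, and use of urgent, emergency or hospital care. Further OMT is not on the list. For the last survey, "The 1-week survey will follow-up on adverse events reported on the 72-hour survey". Survey timing is meant to separate immediate onset (under 24 hours) from delayed onset (24-72 hours), and short, medium and long duration.

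The Statistical Analysis Plan fits generalized linear mixed models "to account for the clustering of responses from patients treated by the same clinician". It mentions no patient-level term and no handling of re-treatment.

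**The concern.** The study aims to describe when reactions to OMT begin, how long they last, and which techniques and regions carry more of them. Each of these needs the symptom to be tied to the right visit. A patient treated on day 0 and again on day 2 may have an immediate reaction to the second visit. The 72-hour survey would record it as delayed onset after the first, and the analysis would link it to the first visit's techniques and regions. If a patient is treated again after 72 hours, a symptom that would have settled may persist or return, and move into the medium or long duration class. The date of the second visit is not among the planned data, so the analysis could not undo either error.

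The second gap concerns people rather than visits. A returning patient still meets the eligibility rule and could be handed a new packet. Two records from one person would then be analysed as if they shared nothing beyond the clinician.

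**Working it through.** **The plan's own figure.** The 1000 comes with no expected incidence, target precision or intraclass correlation, so it cannot be reproduced. With 50 clinicians the mean is at most 1000/50 = 20 participants each. For scale, the simple 95% half-width 1.96 × √(p(1−p)/1000), before clinician clustering, is 0.87 points at p = 2% and 1.35 points at p = 5%.

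**Step 1: added delayed onset.** Let d be the true delayed-onset rate, r the share re-treated before the 72-hour survey, and a the share of those who react to the later visit. With independence, the observed rate is 1 − (1 − d)(1 − r·a). None of d, r or a is in the documents; all values are assumptions.

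| r | a | d | Observed | Added (points) |
|---|---|---|---|---|
| 2% | 10% | 2% | 2.20% | 0.20 |
| 2% | 10% | 5% | 5.19% | 0.19 |
| 5% | 20% | 2% | 2.98% | 0.98 |
| 5% | 20% | 5% | 5.95% | 0.95 |
| 10% | 20% | 2% | 3.96% | 1.96 |
| 10% | 20% | 5% | 6.90% | 1.90 |

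In the third row, 1 − 0.98 × (1 − 0.05 × 0.20) = 1 − 0.98 × 0.99 = 0.0298. The excess of 0.98 points is a little more than the 0.87-point half-width for an event at 2%. The rates a and d must refer to the same event. For one listed symptom, a would be lower than for any symptom, and the excess would shrink in proportion.

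**Step 2: what later re-treatment can do.** The 1-week survey, as described, follows events already reported at 72 hours. Re-treatment after that point therefore adds essentially no new incident events. It acts on duration, and no rate is available to size that effect.

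**Step 3: repeat packets and the overall incidence.** If patients return to the same clinician, both records sit inside one cluster. Their extra correlation enters the estimated between-clinician variance, which widens the interval. A simulation of a logistic random-intercept model used 50 clinicians × 20 packets, 20% incidence, second packets as 20% or 50% of all packets, within-patient correlation 0.3-0.5, clinician ICC 0 to 0.05, and 600 runs per setting. The ratio of model SE to true SD was 0.95-1.06 with repeats and 0.95-1.02 without. Coverage was 93-96% with repeats and 92.5-95% without. Repeats caused no visible narrowing.

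**Step 4: repeat packets and technique or region tests.** These contrasts are largely made within clinicians, so the clinician term does not absorb the pairing. Let f be the share of packets that are second packets, and ρ the within-patient correlation. If a patient receives the same technique both times, the variance is multiplied by 1 + 2fρ. The model SE is then too small by 1 − 1/√(1 + 2fρ), and coverage is 2Φ(1.96/√(1 + 2fρ)) − 1.

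| f | ρ | People | 1 + 2fρ | SE too small by | Coverage |
|---|---|---|---|---|---|
| 10% | 0.5 | 900 | 1.10 | 4.7% | 93.8% |
| 20% | 0.3 | 800 | 1.12 | 5.5% | 93.6% |
| 20% | 0.5 | 800 | 1.20 | 8.7% | 92.6% |
| 50% | 0.5 | 500 | 1.50 | 18.4% | 89.0% |

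Simulation of the technique contrast in the last setting agreed: model SE about 18% too small, coverage about 89%. That setting is extreme, because every person enters twice. If technique varies freely from visit to visit, the effect largely disappears.

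**The case against.** The point rests on silence. The survey forms are not in the documents and may already contain the question. The target is worded as participants, which most readers would take to mean distinct people, and the relatedness rating lets patients discount unrelated symptoms. These objections stand in part: every size above is conditional, and the sponsor may intend one entry per person. The relatedness item does not close the gap, though. As described, it refers to the OMT received without naming a visit, so a patient could truthfully relate a symptom to the second treatment.

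Three stronger readings are tempting and are not supported.

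- A reader might infer that repeat packets make the overall incidence intervals too narrow by the factor in Step 4. That factor applies to a model treating packets as independent. The planned model has a clinician term, and Step 3 shows that it covers patients who return to the same clinician. That they do so is itself an assumption.
- A reader might multiply re-treatment over the whole week, say 10-30%, by a 20% reaction rate and infer 2-6 points of misplaced incidence. The described scope of the 1-week survey rules this out: only re-treatment before the 72-hour survey can add incident events.
- A reader might infer that duplicates could never be found because the download is de-identified. The site tracking sheet, email addresses given by online participants and the payment process could each reveal some. What is missing is a described check.

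**Conclusion.** The concern holds, mainly as a gap in data capture. Further OMT is not in the described survey content and only the index encounter is documented. Reactions to a visit before the 72-hour survey can therefore be misfiled as delayed onset under the wrong techniques and regions, and later visits can lengthen recorded duration. With 2-10% re-treated before 72 hours and 10-20% of those reacting, the addition to delayed onset is about 0.2-2 points. That is modest in absolute terms but can be a large fraction of a rare event. If nobody is re-treated in the window, it is zero.

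Repeat enrolment is secondary. It means fewer than 1000 people and can make technique and region tests anti-conservative when repeats are common and treatment is similar at both visits. At a 10% share of second packets the effect is small. It does not undermine the overall incidence intervals when patients return to the same clinician. The point does not invalidate the study, but the date of a later visit is not in the planned data unless it is asked for.

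**What to change.** 1. Add to the 72-hour and 1-week surveys one dated question: has the participant had further OMT or other manual treatment since the visit this packet refers to, and when?
2. State in the SAP that only events starting before that date are attributed to the index visit, and that event duration is censored there. Report how many participants were re-treated, so that readers can judge the size of the problem.
3. State that each person may enter once, checked by staff against the site tracking sheet. Alternatively, record a site-held patient number beside the packet code and add a patient random effect to the models.

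The first two items matter most. The cost is one survey item, a sentence or two in the protocol and SAP, some censored durations and, under the one-entry rule, slightly slower enrolment. If the survey forms already ask about further treatment, or one entry per person is already intended, the change is only to write this into the plan.

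### No described item records other treatment given at the OMT visit, so reactions to a co-treatment may be counted as OMT adverse events

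*Combined protocol and SAP*

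**What the plan says.** Under *i. Participants*, entry is broad: "All patients from the research sites who receive OMT and who are age 18 years and above will be eligible to participate". The only other stated restriction is language: "Patients who are unable to communicate in English, Spanish, French, German, or Portuguese will be excluded". Nothing limits entry to visits at which OMT was the only treatment, and packets are handed out once the visit is over.

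Under *ii. Recruitment and Procedures*, the site is asked for a record of the encounter, "including the diagnoses treated with OMT, what techniques were performed on that patient, and the clinician's assessment of patient response to the treatment". The patient's consent is framed in the same way, as "consent for the clinician who treated the patient to provide de-identified documentation of the OMT provided".

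Under *iii. Data Collection Instruments*, the Documentation of OMT paragraph describes a grid of techniques against ten body regions, with a response grade for each treated region. Its free-text space has a narrow purpose: "An area will be provided to describe techniques used which are not included in any of these technique groupings". In the Patient-reported Adverse Events paragraph, the 24- and 72-hour surveys ask about the severity, duration and location of each symptom, how far the patient thinks it related to OMT (five levels), and whether it was present in the week before treatment.

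The *Statistical Analysis Plan* estimates the incidence of each event in the whole sample and compares techniques and regions, using generalized linear mixed models that allow for clustering by clinician. It names no covariates and gives no rule for using the relatedness rating.

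**The concern.** The title promises adverse events from OMT. If some patients also had, say, an injection, needling, exercise instruction or a new prescription at the visit, the study as described observes adverse events after visits that include OMT. Many of the listed symptoms (pain, numbness, fatigue, nausea, light-headedness, poor sleep) could also follow such co-treatments, and there is no group without OMT to show the background rate.

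Two results are at stake. The incidence estimates could be too high. The technique and region tests could also be distorted, but only if co-treatment is more common with some techniques or regions than with others. A larger sample would remove neither problem. If the exposure is not recorded, the analysts cannot adjust for it or exclude it afterwards.

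**Working it through.** **Is co-treatment recorded anywhere?** Each described source was checked in turn.

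- Eligibility: adult, received OMT, able to communicate in a listed language. Co-treated patients can enter.
- Clinician record: diagnoses treated with OMT, techniques, regions, response. There is no field for other treatment, and the free text is for unlisted techniques.
- Patient surveys: symptoms, location, relatedness to OMT, prior-week symptoms, use of urgent or hospital care. None asks about other treatment at the index visit. The prior-week item deals with pre-existing symptoms, which is a different matter.
- SAP: no covariate and no relatedness rule.

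**How large could the effect be?** The plan gives no event rate, co-treatment frequency or reaction rate, so it has no figure of its own to reproduce here. Only the 1000 participants and the target of at least 50 clinicians come from the protocol. Everything else below is assumed.

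*Illustration A: risk 20% with OMT alone, 40% with co-treatment, and the relatedness rating removes nothing.* With a share q of visits co-treated, observed incidence = (1 − q) × 0.20 + q × 0.40 = 0.20 + 0.20q.

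| q | Observed incidence | Excess |
|---|---|---|
| 5% | 21% | 1 point |
| 10% | 22% | 2 points |
| 20% | 24% | 4 points |

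The 95% half-width at n = 1000 is 1.96 × √(0.20 × 0.80 / 1000) = 2.5 points. With 1000/50 = 20 patients per clinician and an assumed intraclass correlation of 0.05, the design effect is 1 + 19 × 0.05 = 1.95, and the half-width becomes 2.5 × √1.95 = 3.5 points. Only the 4-point excess is larger than either.

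Technique contrast with no true difference:

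- Co-treatment at 20% against 5% of visits: 24% against 21%; OR = (0.24/0.76)/(0.21/0.79) = 1.19.
- Co-treatment at 30% against 5%: 26% against 21%; OR = (0.26/0.74)/(0.21/0.79) = 1.32.
- Equal co-treatment in both groups: OR = 1.00.

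*Illustration B: a rarer event, with the reaction risk varied.* OMT risk p = 5%, co-treated share c, co-treatment reaction risk r; observed incidence = p + (1 − p) × c × r.

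- Lowest case, c = 10%, r = 10%: 0.05 + 0.95 × 0.01 = 5.95%, an excess of 0.95 points.
- Highest case, c = 20%, r = 30%: 0.05 + 0.95 × 0.06 = 10.7%, an excess of 5.7 points.
- Half-width at p = 5%: 1.35 points, or 1.89 with intraclass correlation 0.05.

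Contrast with co-treatment at 20% against 10% of visits, 500 patients per group, two-sided 5% test, clustering ignored:

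| r | Observed | OR | False-positive rate | OR if ratings removed half of the co-treatment reactions |
|---|---|---|---|---|
| 10% | 6.9% v 5.95% | 1.17 | 9% | 1.09 |
| 30% | 10.7% v 7.85% | 1.41 | 34% | 1.24 |

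With 10% in both groups the OR is 1.00 and the false-positive rate stays at 5%.

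**The case against.** The strongest reply is that the surveys already contain two filters. A patient can mark a symptom as unrelated to OMT, and will often recognise a sore vaccinated arm or nausea after a new tablet. Symptom location can also be set against the treated regions, which helps with local complaints. This stands as far as it goes. It does not help much with a systemic symptom, or with an injection or needling in the region that was also manipulated. The rating item asks only about OMT, and the SAP does not commit to using it.

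A reader might infer more than the documents support, in three ways:

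- *That co-treatment reactions will be counted as OMT events.* The SAP is silent on relatedness, so they may be counted; the text does not settle it.
- *That they will be charged to particular techniques or regions.* This requires unequal co-treatment across techniques or regions, and nothing in the documents shows that. Illustration A's odds ratios rest on a four- to six-fold imbalance.
- *That the data are certainly not captured.* The instruments are summarised rather than reproduced, and the list of encounter data need not be exhaustive. What can be said is that no described item captures co-treatment.

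It is also fair to object that the magnitudes are wholly assumed, and that at 5% to 10% co-treatment the excess in Illustration A lies within sampling error. Both points stand; they bear on the size of the problem and leave the gap in recording as it is. The clinician term in the models is no substitute, since it cannot separate co-treated from other patients of the same clinician.

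**Conclusion.** The point holds as a gap in data collection with an unknown effect. Co-treated adults are eligible, no described item identifies them, and the planned analyses can therefore neither adjust for co-treatment nor leave those visits out. Incidence may be overstated, and the technique and region comparisons may be confounded if co-treatment varies with them.

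Under the assumptions shown, the excess in incidence runs from about 1 point, inside sampling error, to between 4 and 6 points, outside it. Spurious odds ratios run from 1.00 with balanced co-treatment to about 1.4 in the scenarios worked above, and are smaller if the relatedness rating screens out some reactions. The documents do not show where in this range the study would fall. They therefore do not support saying that the results will be biased. They do support recording the exposure, because it cannot be recovered once data collection ends.

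**What to change.** Leave eligibility unchanged, and make these changes before data collection:

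1. Add one line to the OMT documentation form for other treatment at this visit: none / injection / needling / exercise / new or changed medication / other.
2. Extend the consent wording to cover it, since consent now reaches only the clinician's record of the OMT.
3. State in the SAP how the relatedness rating enters the definition of an adverse event.
4. Report incidence for all visits and, as sensitivity analyses, for OMT-only visits and by relatedness level.
5. Include co-treatment as a covariate in the technique and region models.

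The cost is a small change to the form and to the consent text, and a few extra analyses. The OMT-only estimate will rest on fewer patients. Their case mix may also differ if co-treatment follows diagnosis or severity, so that estimate should be read beside the all-visit figure and not in its place.
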